6.5. Prior and Concomitant Medications

Prior medications are defined as medications that started before first study drug administration and either stopped before or continued after first study drug administration. Concomitant medications are defined as medications that are being taken while on study drug through 30 days after last dose or through the Follow-Up Period (Week 16). Medications that are ongoing on the date of the first administration of study drug will be classified as both prior and concomitant. Any medication that cannot be confirmed as stopping before the start of study drug will be classified as both a prior and a concomitant medication. Imputation of partial dates is defined in Appendix 2.

Prior and concomitant medications will be summarized separately and the number and percentage of patients in each treatment group who took at least one prior (concomitant) medication as well as the number and percentage of patients who took each type of medication will be summarized by Anatomic Therapeutic Class (ATC) Level 2 and preferred name for the Safety Analysis Set. If a patient has more than one occurrence of the same preferred name, then the preferred name will be counted only once for that patient. Similarly, if a patient has more than one preferred name within ATC Level 2, then the patient will be counted only once in that ATC Level 2.

Any medications with potential beneficial impact on NASH outcome and steatohepatitis will be presented in a separate by-patient listing.

CONFIDENTIAL

Statistical Analysis Plan CONFIDENTIAL Labcorp Drug Development Study: 000000231152 Protocol Reference: TERNCB-2002

7. Efficacy Analyses

7.1. Adjustments for Covariates

The Baseline value will be used as a covariate in each ANCOVA model.

7.2. Handling of Dropouts or Missing Data

Primary analyses will be based on observed data. For the primary endpoint, a sensitivity analysis will be conducted for patients who do not complete the Week 12 visit, where the last on-treatment value, including any values collected at unscheduled visits, will be carried forward (LOCF) and used for Week 12.

7.3. Interim Analyses and Data Monitoring

No interim analysis or data monitoring committees are planned for this study.

7.4. Multicenter Studies

The randomization is not stratified by site. Likewise, analyses of data will not be stratified by study site.

7.5. Use of an "Efficacy Subset" of Patients

Not Applicable.

7.6. Multiple Comparisons/Multiplicity

Table 6 depicts the pairwise comparisons which will be performed denoted by "X".

Table 6 Pairwise Comparison for Display

	101	501 (1)	501 (3)	501 (6)	101+501 (3)	101+501 (6)
Placebo	X	X	X	X	X	X
501 (3)					X	
501 (6)						X

Table 7 depicts the order or comparison for the hierarchical testing strategy.

Statistical Analysis Plan CONFIDENTIAL Labcorp Drug Development Study: 000000231152 Protocol Reference: TERNCB-2002

Table 7 Hierarchical Testing Strategy

MRI-PDFF						
	101	501 (1)	501 (3)	501 (6)	101+501 (3)	101+501 (6)
Placebo		3	2	1	5	4
501 (3)					7	
501 (6)						6
cT1						
	101	501 (1)	501 (3)	501 (6)	101+501 (3)	101+501 (6)
Placebo	4	3	2	1	6	5
501 (3)					8	
501 (6)						7

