9.1. Statistical Hypotheses

The primary statistical analysis will test whether the mean relative change from baseline in MRI-PDFF is (H₁) or is not (H₀) different between placebo and TERN-501 monotherapy. Secondary statistical analyses will test whether the mean relative change from baseline in MRI-PDFF is (H₁) or is not (H₀) different between placebo and TERN-501+TERN-101. Similarly, statistical analyses of cT1 will test whether the mean change from baseline is (H₁) or is not (H₀) different between placebo and TERN-501 monotherapy and between placebo and TERN-501+TERN-101. In addition, exploratory analyses will evaluate all pairwise comparisons between the different TERN-501 doses and of TERN-101 compared to placebo and will be considered nominal and descriptive.

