9.4.4. Exploratory Endpoints

9.4.4.1. Efficacy Endpoints

All exploratory efficacy analyses will be performed on Efficacy Analysis Set. Exploratory analyses will evaluate all pairwise comparisons between the 7 treatment groups and will be considered nominal and descriptive.

The primary and secondary endpoints evaluate Week 12 MRI-PDFF and cT1, while exploratory endpoints will summarize and analyze other applicable time points and additional treatment group comparisons of TERN-501+TERN-101 to TERN-501 monotherapy and TERN-101 monotherapy in the same manner specified for the primary and secondary endpoints. Additional details will be specified in the SAP.

Change (and separately percent change) from baseline in liver enzymes, NASH and fibrosis biomarkers, and liver stiffness will be summarized and analyzed at applicable time points using the same ANCOVA model specified for the primary endpoint.

FAST score will be calculated based on liver stiffness and AST values (Newsome 2020).

MRI-PDFF responders will be defined as any patient with a relative decrease of at least 30%. Non-responders will be defined as any patient who did not have at least a 30% relative decrease. The number and percentage, with associated two-sided exact (Clopper-Pearson) 95% CI, of patients in each category (response, nonresponse) will be presented by treatment group at applicable time points. A Chi-square test will be used to compare treatment groups.

cT1 responders will be defined any patient with a decrease of at least 80 msec. Non-responders will be defined any patient who did not have at least an 80 msec decrease. cT1 response will be summarized and analyzed at applicable time points in the same manner as specified for MRI-PDFF.

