2.2.3. Exploratory Objectives

- To explore the effect of TERN-501 monotherapy on efficacy and markers of target engagement compared to placebo
- To explore the effect of TERN-501+TERN-101 on efficacy and markers of target engagement, compared to placebo and/or each monotherapy
- To evaluate the pharmacokinetics of TERN-501 and TERN-101 administered alone and in combination

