7.8. MRI-PDFF Analyses

For all MRI-PDFF analyses, relative change from baseline and absolute change in MRI-PDFF will be analyzed and reported according to Section 7.7 using the pairwise comparisons in Section 7.6 for the efficacy and per protocol analysis sets.

An additional sensitivity analysis of relative change in MRI-PDFF at Week 12 using a last observation carried forward (LOCF) approach will be performed according to Section 7.7 using the pairwise comparisons in Section 7.6 for the efficacy analysis set. The LOCF endpoint will be labelled "End of Treatment". For the LOCF analysis, patients who complete Week 12, the Week 12 value will be used. For patients who do not complete treatment, the last value on treatment will be used. Otherwise, the Week 12 response will be missing.

An analysis of MRI-PDFF relative change responders using the pairwise comparisons in Section 7.6 will be performed using the efficacy analysis set. Responders will be defined as any patient with a relative decrease of at least: (1) 30% (i.e., ≤-30%), (2) 40%, (3) 50% at weeks 6 and 12. Non-responders will be defined as any patient who did not have at least a relative decrease for each specific analysis. The frequency and percentage of responders along with a two-sided exact (Clopper-Pearson) 95% CI for the percentage of responders will be presented. For each pairwise comparison, the difference in percentage of responders, 95% CI, and p-value using a chi-square test will be presented.

7.8.1. cT1

For all cT1 analyses, change from baseline in cT1 will be analyzed and reported according to Section 7.7 using the pairwise comparisons in Section 7.6 for the efficacy and per-protocol analysis sets.

An analysis of cT1 change responders using the pairwise comparisons in Section 7.6 will be performed for the efficacy analysis set. Responders will be defined as any patient with a decrease of at least 80 msec at weeks 6 and 12. Non-responders will be defined as any patient who did not have at least a 80 msec decrease for each specific analysis. The frequency and percentage of responders along with a two-sided exact (Clopper-Pearson) 95% CI for the percentage of responders will be presented. For each pairwise comparison, the difference in percentage of responders, 95% CI, and p-values using a chi-square test will be presented.

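### SAP Table 6 omits the combination-versus-TERN-101 comparison that Protocol 9.4.4.1 plans for MRI-PDFF and cT1, while SAP Section 10 reports no change

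*SAP*

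**What the plan says.** Protocol 9.4.4.1 extends the Week 12 MRI-PDFF and cT1 analyses to other time points and to "additional treatment group comparisons of TERN-501+TERN-101 to TERN-501 monotherapy and TERN-101 monotherapy", analysed as for the primary and secondary endpoints. It then adds: "Additional details will be specified in the SAP". The same section also makes a wider statement: "Exploratory analyses will evaluate all pairwise comparisons between the 7 treatment groups and will be considered nominal and descriptive". Protocol 9.1 is narrower; there, "exploratory analyses will evaluate all pairwise comparisons between the different TERN-501 doses and of TERN-101 compared to placebo".

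The SAP keeps the exploratory objective of studying the combination "compared to placebo and/or each monotherapy" (SAP 2.2.3). SAP 7.6 then fixes the list: "Table 6 depicts the pairwise comparisons which will be performed denoted by" an X. Eight pairs are marked: the six active arms against placebo, and each combination against the TERN-501 arm of the same dose. TERN-101 appears only as a column against placebo.

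The endpoint sections rely on that list. SAP 7.8: "An analysis of MRI-PDFF relative change responders using the pairwise comparisons in Section 7.6 will be performed using the efficacy analysis set". SAP 7.8.1: "change from baseline in cT1 will be analyzed and reported according to Section 7.7 using the pairwise comparisons in Section 7.6". SAP Section 10 states that the analyses planned in the protocol were not changed.

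**The concern.** Protocol 2.2.2 justifies the combination by the prospect of doing better than either drug alone, and Protocol 4.3 describes the TERN-101 10 mg arm as a monotherapy comparator. About 20 patients are randomised to it. Two exploratory questions follow: what TERN-101 adds to TERN-501, and what TERN-501 adds to TERN-101. The SAP plans an estimate for the first only.

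For the second, a reader could subtract the reported LS means. The standard error, the confidence interval and the responder difference would then be calculations made outside the plan. Because Section 10 reports no change, nothing on record says whether the comparison was dropped on purpose or why.

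**Working it through.** This is mainly a comparison of texts. The arithmetic only gives its scale.

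**1. Is the comparison in both documents?**

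| Comparison | Protocol | SAP Table 6 |
|---|---|---|
| Combination vs placebo | 9.4.3 (secondary) | marked, both doses |
| Combination vs TERN-501 | 9.4.4.1, named | marked, matched dose only |
| Combination vs TERN-101 | 9.4.4.1, named | absent |
| TERN-101 vs placebo | 9.1, named | marked |
| TERN-501 doses with each other | 9.1, named | absent |

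A table-extraction fault is unlikely: both panels of Table 7 have the same three rows (placebo, 501 3 mg, 501 6 mg). Sections 7.7, 7.8 and 7.8.1 do not add the missing pair.

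**2. Pair count.** Seven arms give 7 × 6 / 2 = 21 pairs. Table 6 marks 6 + 2 = 8, so 21 − 8 = 13 are absent. These include the two combination-vs-TERN-101 pairs and the three TERN-501 dose pairs. Adding the two combination-vs-TERN-101 pairs gives 10 of 21.

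**3. Reproducing the plan's power figures.** Inputs from Protocol 9.2: SD 22 percentage points (MRI-PDFF) and 82 msec (cT1), 20 per arm, two-sided alpha 0.05. Noncentral t with 38 df and noncentrality d / (SD × √(2/n)):
- MRI-PDFF, d = 23: 23 / 6.96 = 3.31, power 89.6% (stated: about 90%).
- cT1, d = 77: 77 / 25.93 = 2.97, power 82.5% (stated: about 82%).

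Both reproduce.

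**4. Precision of the omitted contrast.** SE = SD × √(2/n). The SAP 7.7 ANCOVA has seven arms and one covariate, so df = 7n − 8, and the half-width is t × SE. The SDs are used with no reduction for the baseline covariate. The values n = 18 and n = 16 are assumptions, shown because SAP 7.2 analyses observed data.

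| n per arm | df | t | SE, PDFF | half-width, PDFF | SE, cT1 | half-width, cT1 |
|---|---|---|---|---|---|---|
| 20 | 132 | 1.978 | 6.96 | 13.8 points | 25.93 | 51.3 msec |
| 18 | 118 | 1.980 | 7.33 | 14.5 points | 27.33 | 54.1 msec |
| 16 | 104 | 1.983 | 7.78 | 15.4 points | 28.99 | 57.5 msec |

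These apply to any two-arm contrast in the trial, so the omitted pairs would be as precise as the retained ones.

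**5. Which side is more likely to show a difference?** This step depends on the additivity that Protocol 9.2 assumes; the documents do not state these results. Combination minus TERN-101 then equals the TERN-501 effect, 23 points or 77 msec, with power 89.6% and 82.5%. The retained combination-vs-TERN-501 pairs imply 36 − 23 = 13 points and 134 − 77 = 57 msec, with power 44.5% and 57.2%.

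**The case against.** The best defence is that the protocol gives the SAP room. Protocol 9.4 calls itself a summary and leaves the details to the SAP, 9.4.4.1 repeats this beside the comparison in question, and the objective's and/or is permissive. Protocol 9.1 does not mention combination versus TERN-101 at all. Cutting a long list of nominal pairs to a short one is ordinary SAP work, and because Tables 6 and 7 share the same asymmetry, the choice looks deliberate. The loss is also modest: per-arm LS means, SEs and intervals are reported, as are responder counts, so a reader can obtain the differences and approximate the interval. Finally, SAP 7.7 says its analyses include the Table 6 pairs, which is not strictly exclusive, and the table shells are not available here.

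Much of this stands as a limit on the weight of the point. It does not remove it. Section 9.4.4.1 commits to the comparison and names both monotherapies; room for detail does not cover dropping a named comparison without record. SAP 7.6 presents Table 6 as the pairs to be performed. If the choice was deliberate, Section 10 is where it should have been declared.

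**Conclusion.** The concern holds. Table 6 omits two pairs that Protocol 9.4.4.1 names for MRI-PDFF and cT1, and the no-change statement in SAP Section 10 is incorrect. The consequence is limited to exploratory, descriptive results; every primary and secondary comparison is intact. What is lost is a planned difference, SE, 95% CI and responder difference for the contribution of TERN-501 on top of TERN-101. The half-widths of 13.8 points and 51 msec rest on the plan's SDs and complete data from 20 per arm, and need no assumed effect. The power contrast in step 5 is context only, since it depends on additivity. This should be fixed but does not threaten the trial's main conclusions.

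**What to change.** - **Table 6.** Add a 101 row with an X under 101+501 (3) and under 101+501 (6). Label both contrasts nominal and descriptive, and leave Table 7 as it is.
- **Scope.** Report the contrasts at least for MRI-PDFF and cT1: LS mean difference, SE and 95% CI for change (relative change for MRI-PDFF), and difference with 95% CI for responders. Other endpoint sections also use Table 6, so add a sentence if the row is to apply only to these two. Say that any responder chi-square p-value for these pairs is nominal, and state whether Week 6 is included, since Protocol 9.4.4.1 reaches beyond Week 12 and SAP 7.7 applies the Table 6 pairs at Week 12.
- **Section 10.** Record what will still not be done: the three TERN-501 dose pairs named in Protocol 9.1, and the reduction of the all-pairs statement in Protocol 9.4.4.1 to the Table 6 list, with the reason.

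The cost is two more contrasts per affected table from an ANCOVA that already contains all seven arms, plus updated shells. No new data are needed and no alpha is taken from the Table 7 tests. If the sponsor prefers not to add the contrasts, recording their omission and the reason in Section 10 would remove the contradiction, but would leave that half of the combination question without a planned estimate.

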7.7. Analysis and Reporting of Change and Relative Change from Baseline

Analysis of change and relative change will be performed using a type III sum of squares ANCOVA model with treatment group as a fixed effect and baseline covariate, where applicable. Least squares (LS) means and standard errors (SE) as well as 95% confidence intervals (CIs) will be presented for each treatment group at each scheduled visit.

LS estimates of the mean difference, SE, and 95% CI between each TERN active treatment group versus placebo comparison will be presented at scheduled visits. Analyses will include the pairwise comparisons in table 6 of Section 7.6 at week 12, unless otherwise specified. Relative change will include LS means, SE, and 95% CI but only MRI-PDFF relative change will include inferential statistics.

Table displays:

- (1) Observed result descriptive statistics, as described in Section 3.1, will be displayed within the same table.
- (2) All scheduled visits should be reported.
- (3) Pooling of treatment group should not be performed or displayed unless noted otherwise.

7.8. MRI-PDFF Analyses

For all MRI-PDFF analyses, relative change from baseline and absolute change in MRI-PDFF will be analyzed and reported according to Section 7.7 using the pairwise comparisons in Section 7.6 for the efficacy and per protocol analysis sets.

An additional sensitivity analysis of relative change in MRI-PDFF at Week 12 using a last observation carried forward (LOCF) approach will be performed according to Section 7.7 using the pairwise comparisons in Section 7.6 for the efficacy analysis set. The LOCF endpoint will be labelled "End of Treatment". For the LOCF analysis, patients who complete Week 12, the Week 12 value will be used. For patients who do not complete treatment, the last value on treatment will be used. Otherwise, the Week 12 response will be missing.

An analysis of MRI-PDFF relative change responders using the pairwise comparisons in Section 7.6 will be performed using the efficacy analysis set. Responders will be defined as any patient with a relative decrease of at least: (1) 30% (i.e., ≤-30%), (2) 40%, (3) 50% at weeks 6 and 12. Non-responders will be defined as any patient who did not have at least a relative decrease for each specific analysis. The frequency and percentage of responders along with a two-sided exact (Clopper-Pearson) 95% CI for the percentage of responders will be presented. For each pairwise comparison, the difference in percentage of responders, 95% CI, and p-value using a chi-square test will be presented.

7.8.1. cT1

For all cT1 analyses, change from baseline in cT1 will be analyzed and reported according to Section 7.7 using the pairwise comparisons in Section 7.6 for the efficacy and per-protocol analysis sets.

An analysis of cT1 change responders using the pairwise comparisons in Section 7.6 will be performed for the efficacy analysis set. Responders will be defined as any patient with a decrease of at least 80 msec at weeks 6 and 12. Non-responders will be defined as any patient who did not have at least a 80 msec decrease for each specific analysis. The frequency and percentage of responders along with a two-sided exact (Clopper-Pearson) 95% CI for the percentage of responders will be presented. For each pairwise comparison, the difference in percentage of responders, 95% CI, and p-values using a chi-square test will be presented.

7.9. Liver Enzymes (ALT, AST, GGT)

For ALT, AST, and GGT analyses, change from baseline will be analyzed according to Section 7.7 using the pairwise comparisons in Section 7.6 for the efficacy analysis set.

An analysis of ALT change responders using the pairwise comparisons in Section 7.6 will be performed for the efficacy analysis set. Responders will be defined as any patient with a decrease of at least 17 U/L from baseline at weeks 6 and 12. Non-responders will be defined as any patient who did not have at least a decrease for each specific analysis. The frequency

CONFIDENTIAL

and percentage of responders along with a two-sided exact (Clopper-Pearson) 95% CI for the percentage of responders will be presented. For each pairwise comparison, the difference in percentage of responders, 95% CI, and p-value using a chi-square test will be presented.

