Note: In patients in whom there is no known history of thyroid disease and who are not on thyroid hormone replacement medication, if TSH is up to 1.5 x ULN at Screening with normal free T4, 1 repeat test is allowed to confirm the elevation in TSH. If TSH and free T4 are normal upon repeat testing and there is no clinical suspicion of thyroid disease or history of elevated TSH, the patient may be included. All thyroid axis testing should be performed in the morning, approximately at the same time.

- 8. Total bilirubin > 1.2 mg/dL
- 9. Albumin < 3.5 g/dL
- 10. INR > 1.2 in patients who are not on anticoagulant therapy
- 11. ALT or AST > $5 \times ULN$
- 12. Unstable elevated ALT or AST: Patients with ALT or AST > 60 IU/L must have evidence of a stable value over at least a 2-week time period prior to randomization as evidenced by one of the following:
 - a. Comparison to a historical value, if available, obtained within 2 to 12 weeks prior to the Screening visit: Screening value must be $\leq 30\%$ higher than a documented historical value (Note: the historical value must be $\leq 5 \times ULN$)

OR

b. Repeat value at least 2 weeks after the Screening value: Repeat value should be $\leq 30\%$ higher than the value from the Screening visit, and the repeat value must be $\leq 5 \times \text{ULN}$ (Note: repeat only the analyte(s) that is/are > 60 IU/L at Screening)

Note: If the Investigator has clinical suspicion for acute liver injury in a patient for other reasons, the patient should be excluded after discussion with the Medical Monitor.

Note: The MRI-PDFF and cT1 may proceed on the basis of the initial ALT value at Screening, given all other eligibility criteria are met, but randomization should not occur prior to confirmation of ALT and/or AST stability as specified above.

- 13. ALP > 1.5 x ULN
- 14. Platelet count < 150,000 /mm³
- 15. $eGFR < 60 \text{ mL/min}/1.73 \text{m}^2$ (Refer to Appendix 5 for the eGFR formula)
- 16. Weight loss of > 5% total body weight within 3 months prior to Screening
- 17. History of a malignancy within 2 years of screening, with the following exceptions:

CONFIDENTIAL

- a. Adequately treated carcinoma in situ of the cervix
- b. Adequately treated basal or squamous cell cancer or other localized non-melanoma skin cancer
- 18. Prior or planned (during the study period) bariatric surgery (e.g., gastroplasty, roux-en-Y gastric bypass)
- 19. Type 1 diabetes

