- Antithrombotic medications defined by WHODD SDG of "Antithrombotic drugs"
- Antidiabetic medications defined by the WHODD SDG of "Drugs used in diabetes"
- Hormonal contraceptives defined by the WHODD SDG of "Drugs used in Hormonal contraception"
- Vitamin E defined by the WHODD drug codes beginning in "001105" or if "VITAMIN E" is found in the preferred drug name
- Pioglitazone or other PPARγ agonists defined by WHODD ATC level 4 A10BD and A10BG
- o GLP-1 analogues defined by WHODD ATC level 4 code (term) A10BJ (Glucagon-like peptide-1 [GLP-1] analogues)
- DPP-4 inhibitors defined by WHODD ATC level 4 code (term) A10BH (Dipeptidyl peptidase 4 [DPP-4] inhibitors)
- SGLT2 inhibitors defined by WHODD ATC level 4 code (term) A10BK (Sodium-glucose co-transporter 2 [SGLT2] inhibitors)

The following baseline laboratory tests will be summarized as continuous variables and as frequencies for categorizations described:

- Baseline ALT level (U/L):
 - $\circ \le 60 \text{ U/L versus} > 60 \text{ U/L (overall and by sex)}$
 - < 2x ULN versus $\ge 2x$ ULN to < 5x ULN
- Baseline AST level (U/L): The same subgroups as specified for ALT above will be used
- Baseline GGT level (U/L): $\leq ULN$, > ULN
- Baseline ALP level (U/L): $\leq ULN$, > ULN
- Baseline total bilirubin level (mg/dL)
- Baseline fasting HDL cholesterol (mg/dL)
- Baseline fasting LDL cholesterol (mg/dL)

CONFIDENTIAL

- Baseline fasting total cholesterol (mg/dL)
- Baseline fasting triglycerides (mg/dL)
- Baseline fasting glucose level (mg/dL)
- HbA1c (%): $< 6.5\%, \ge 6.5\%$
- Baseline platelet count $(10^9/L)$:
- Baseline free T3 (FT3)
- Baseline total T3
- Baseline free T4
- Baseline total T4
- Baseline TBG
- Baseline rT3
- Baseline FT3/rT3

Demographics and baseline characteristics will be summarized by treatment group and overall, for the Safety, Efficacy, and Per Protocol Analysis Sets.

All demographic and baseline characteristics data will be presented in by-patient data listings.

No inferential statistical comparisons will be performed.

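### The ALT responder comparison in SAP 7.9 uses a fixed 17 U/L fall and an unadjusted chi-square although entry sets no lower ALT limit; stratifying by baseline ALT would be a small, cheap improvement

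*SAP*

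**What the plan says.** SAP 7.9 defines ALT response in absolute units: "Responders will be defined as any patient with a decrease of at least 17 U/L from baseline at weeks 6 and 12". On the population it says "An analysis of ALT change responders using the pairwise comparisons in Section 7.6 will be performed for the efficacy analysis set", and on the method "For each pairwise comparison, the difference in percentage of responders, 95% CI, and p-value using a chi-square test will be presented". It names no baseline ALT floor, stratum or covariate.

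Protocol 5.2 excludes ALT or AST above 5 x ULN and adds a stability requirement: "Unstable elevated ALT or AST: Patients with ALT or AST > 60 IU/L must have evidence of a stable value". That requirement applies only above 60 IU/L. Neither Protocol 5.1 nor 5.2 sets a minimum ALT. SAP 2.1.4 describes equal allocation to seven groups and mentions no stratification by ALT.

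SAP 6.2 tabulates baseline ALT at or below versus above 60 U/L, but ALT is not among the subgroups in SAP Section 5.

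The same section also plans a continuous analysis: "For ALT, AST, and GGT analyses, change from baseline will be analyzed according to Section 7.7". SAP 7.1 adds: "The Baseline value will be used as a covariate in each ANCOVA model".

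**The concern.** A fixed fall in U/L is a different hurdle for each patient. With no lower entry limit, some patients would need to lose most of their ALT to count as responders, while others qualify with a modest relative change. The SAP's other two responder definitions are less exposed. The MRI-PDFF cut is relative. The cT1 cut is absolute, but entry requires at least 800 msec, so 80 msec is never more than 80/800 = 10% of the entry value.

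An arm's ALT responder rate therefore depends on its mix of baseline values as well as on treatment, and the planned test ignores a baseline value that is already collected. With about 20 patients per arm, chance differences in that mix are to be expected. One placebo arm serves six of the eight pairwise comparisons in SAP Table 6, so an unlucky placebo baseline would shift all six in the same direction. At stake are the precision and readability of this one table.

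**Working it through.** **Inputs from the documents.** Cut of 17 U/L (SAP 7.9); n = 20 per arm (Protocol 9.2); two-sided 0.05 (SAP 3.1); 60 U/L category (SAP 6.2). Neither document gives a baseline ALT distribution, an ULN in U/L, or a power for this analysis.

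**The plan's own power figure.** For MRI-PDFF, 23 / (22 x sqrt(2/20)) = 3.31. Power is 91% by the normal approximation and 90% by noncentral t, so the stated figure of about 90% reproduces. It says nothing about ALT.

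**Required relative fall (no assumptions).** Formula: 17 / baseline.

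| Baseline ALT (U/L) | 17 | 25 | 35 | 40 | 60 | 100 | 120 |
|---|---|---|---|---|---|---|---|
| Required fall | 100% | 68% | 49% | 43% | 28% | 17% | 14% |

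**Chance of response at a given baseline.** Assume a true relative fall d and a log-normal post/baseline ratio with log-SD 0.25. Then P = Φ{ln[(1 − 17/b)/(1 − d)] / 0.25}.
- d = 30%: 0.1% at 25, 11% at 35, 54% at 60 and 79% at 120 U/L. For example, at 35: ln(0.514/0.70)/0.25 = −1.23, giving 11%.
- d = 20%: 4% at 35, 9% at 40, 33% at 60 and 56% at 100 U/L.

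**Noise from chance imbalance (simulation).** Assume log-normal baseline ALT with log-SD 0.5. The SD of the difference in mean log baseline between two arms is 0.5 x sqrt(2/20) = 0.158. With a 20% drug effect:

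| Assumed median ALT (U/L) | 35 | 45 | 60 |
|---|---|---|---|
| Mean drug difference (points) | 8.6 | 14.1 | 20.7 |
| Shift from a 1-SD imbalance (points) | 3.0 | 3.8 | 4.8 |
| Ratio | 35% | 27% | 23% |

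Imbalance explains about 13 to 15% of the variance of the difference.

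**Type I error of the planned chi-square.**
- No fall in either arm, medians 35 / 45 / 60: two-sided rejection in 0.2%, 2.0% and 3.6% of trials.
- Median 50: 2.8% with no fall, 4.1% with a 5% fall in both arms and 4.9% with a 30% fall in both arms.
- Only pairs where active is more than 0.2 higher in mean log baseline (0.2/0.158 = 1.27 SD, about 10% of pairs), median 50: rejection in favour of active is 4.1%, 5.8% and 11.3% for the same three cases, against a nominal 2.5%. Stratifying at 60 U/L brings the last figure to about 5%.

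**Power, chi-square versus stratified at 60 U/L (median 50).**
- 30% versus 5% fall: about 55% rises to 60%.
- 35% versus 5% fall: about 75% rises to 79 or 80%.
- 30% versus 5% fall, only pairs where active is more than 0.2 lower in mean log baseline (again about 10%): 24% rises to 48%.

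**Adjusting for log baseline ALT instead.** With a 20% effect and median 45, the mean difference is unchanged (0.144 versus 0.142) and its SD falls from 0.105 to 0.098.

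**Restricting to baseline above 60 U/L.** This keeps about 14%, 28% or 50% of patients for medians 35 / 45 / 60, or roughly 3, 6 or 10 per arm of 20. At median 45, placebo versus 20%-effect rates become 17% versus 47%, compared with 6% versus 21% in all patients.

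**The case against.** The strongest defence is that little rests on this table. ALT is an exploratory parameter, the responder endpoints listed in both documents are only MRI-PDFF and cT1, and ALT is absent from the hierarchy in SAP Table 7. Protocol 9.4.4.1 treats exploratory comparisons as nominal. SAP 7.9 already has a baseline-adjusted ANCOVA of ALT change, which under the assumptions above has about 66 to 67% power for a 20% effect, against 11 to 37% for the chi-square. Baseline ALT will be tabulated by arm, so an imbalance will be visible. All of this stands, and it keeps the point minor. It does not repair the responder table, which will still carry percentages, intervals and p-values at two visits.

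A reader might draw stronger conclusions that the documents do not support:
- **That patients with normal ALT cannot respond.** Response is arithmetically impossible only below 17 U/L. At 35 to 40 U/L it needs a 43 to 49% fall, which is unlikely but possible. With no ULN stated in U/L, what counts as normal is itself an assumption.
- **That arm rates follow baseline ALT as much as drug effect.** A typical imbalance moves the difference by about a quarter to a third of a 20% effect.
- **That the test produces excess false positives.** The 11% figure applies only to the most unbalanced tenth of pairs, in one direction, with a 30% fall in both arms, placebo included.
- **That every continuous efficacy analysis adjusts for baseline.** SAP 7.18.2 analyses the 7αC4 and FGF19 parameters by ANOVA with treatment group alone.

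**Conclusion.** The point holds as a minor improvement. The definition and the test are as described, and the required relative fall varies from 68% at 25 U/L to 14% at 120 U/L by arithmetic alone. Low-ALT patients dilute the responder rate, and ignoring baseline leaves avoidable noise in the between-arm difference.

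The loss is about 2 to 5 points of power in most effect scenarios, with a misleading contrast possible when baseline ALT is clearly unbalanced. There is no systematic bias and no overall inflation of type I error. The power and imbalance figures rest on assumed log-normal ALT (medians mainly 40 to 60 U/L, log-SD 0.5, within-patient log-SD 0.25) and would change with the real distribution. No primary or secondary conclusion is affected.

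**What to change.** In SAP 7.9, replace the chi-square with a Cochran-Mantel-Haenszel test and a stratified risk difference with its 95% CI, using the baseline ALT categories already in SAP 6.2 (at or below versus above 60 U/L). A logistic model with treatment and log baseline ALT is an acceptable alternative. Show responder counts and rates by the same two categories at Weeks 6 and 12.

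Keep all Efficacy Set patients as the main population. A table limited to elevated baseline ALT can be supportive only, because it could leave just a few patients per arm.

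The cost is a sentence or two of SAP text and a small programming change. The drawback is sparse strata at 20 per arm. Sparseness is already present in the planned test: with a 20% effect, at least one expected cell count is below 5 in 65 to 100% of simulated trials.
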